1. INTRODUCTION

Human Immunodeficiency Virus-1 (HIV) is a life threatening and serious infection throughout the world. The World Health Organization estimates between 30-43 million people are living with HIV worldwide. The natural progression of the disease cripples the immune system, leading to unchecked infections and ultimately death.

With the advent of highly active antiretroviral therapy (HAART), we saw HIV transform from a terminal infection into a chronic disease that was managed with drugs. This transformation, however, required three drug combination regimens to prevent HIV from developing resistance to the drug. This resulted in numerous pills taken at strict dosing intervals frequently throughout the day. As treatments evolved, therapy required fewer pill numbers and decreased dosing intervals. This trend eventually gave way to efavirenz/emtricitabine/tenofovir disoproxil fumarate (EFV/FTC/TDF) co-formulated into a single tablet, ATRIPLA®. This was the advent of the single tablet regimen—one pill, once a day. ATRIPLA® has many years of proven efficacy and improved patient adherence¹

With the continued evolution of potent HAART, virologically suppressed HIV-infected patients are often switched to safer and better tolerated drugs¹. Both older patients with age associated comorbidities and younger patients, who can fairly expect to be on antivirals for many years to come, are rightly concerned about side effects and toxicities of long term exposure to highly potent medications. Patients depend on their providers to optimize long term safety and tolerability in their antiretroviral therapy.

1.1 Rationale for the Study

Therapeutic dosage of the tenofovir disoproxil fumarate (TDF) component of ATRIPLA® requires plasma concentrations of the drug that are associated with nephrotoxicity and decreased bone mineral density³. Tenofovir alafenamide fumarate (TAF) has a unique metabolism that results in higher intracellular levels of the active phosphorylated moiety tenofovir-diphosphate². Compared with TDF, the therapeutic dosage of TAF reduces tenofovir plasma concentrations by over 90%. This reduction in plasma concentration results in decreased renal and bone risks. TAF has the potential to improve on the efficacy and safety profile of TDF.

Efavirenz, another component of ATRIPLA® is widely associated with neuropsychiatric side-effects, including sleep disturbances, depression, and anxiety⁴. Switching from Efavirenz to an integrase inhibitor is associated with improvements in mood^{5,6}.

Bictegravir (BIC) is a novel, once daily integrase inhibitor. It has been shown to have potent antiviral activity, a favorable pharmacokinetic profile, good tolerability and an improved resistance profile when compared to previous integrase inhibitors. ^{10,11.} In a phase 2 trial investigating previously untreated people with HIV, bictegravir plus emtricitabine and tenofovir alafenamide (BIKTARVY®) vs dolutegravir, plus emtricitabine and tenofovir alafenamide both showed high efficacy up to 24 weeks and both regimens were well tolerated. ¹²

Additionally, switching HAART experienced patients to BIKTARVY® has been shown to be non-inferior to continuation of regimens containing Atazanavir or Darunavir, when they were given with either lamivudine/abacavir or FTC/TDF.¹³

We plan to evaluate in a real world setting the efficacy, safety and tolerability of switching from the older, established single tablet regimen of ATRIPLA® (EFV/FTC/TDF) to a new single tablet regimen of BIKTARVY® (BIC/FTC/TAF).

Within the limitations of a real-world study, we have attempted to replicate the protocol of Gilead Science's Phase 3 study evaluating a switch to BIC/FTC/TAF from dolutegravir plus either FTC/TAF or FTC/TDF¹⁴. This will have the potential benefit of comparing different regimen switches as well as potentially adding robustness to the body of data regarding BIC/FTC/TAF.

2. STUDY OBJECTIVES

2.1. The primary objective of the study is:

To evaluate the proportion of participants with virologic failure determined by HIV-1 RNA ≥ 50 copies/mL at week 48 in virologically suppressed patients with HIV-1 infection switching from ATRIPLA® to BIKTARVY®.

2.2. The secondary objectives of the study are:

- To determine the safety of switching from ATRIPLA® to BIKTARV®Y in virologically suppressed
 patients with HIV-1 infection as determined by the proportion of participants with virologic failure, a
 rise in serum creatinine values, a change in lipid parameters, and change in CD4 cell count from
 baseline.
- To determine the efficacy of switching from ATRIPLA® to BIKTARVY® in virologically suppressed
 patients with HIV-1 infection as determined by the proportion of participants with HIV-1 RNA < 50
 copies/MI.
- To evaluate tolerability, durability of BIKTARVY® in virologically suppressed patients with the aid of 2 Patient Reported Outcomes (PRO) questionnaires (see appendix 3).

3. STUDY ENDPOINTS

3.1. Primary Endpoint

• The primary efficacy endpoint is the proportion of subjects that have HIV-1 RNA ≥ 50 copies/mL at week 48, as defined by the FDA snapshot analysis.

3.2. Secondary Endpoints

- The proportion of subjects that have HIV-1 RNA < 50 copies/mL at week 48, as defined by the FDA snapshot analysis.
- The change from baseline in serum creatinine at Week 48
- The change from baseline in CD4 cell count at Week 48
- The change from baseline in lipid parameters at Week 48
- The change in responses to the PROs from baseline at Week 4, 12, and 48

4. STUDY DESIGN

4.1. Study Summary

Prospective 48 week single cohort study to evaluate the efficacy and safety of switching from ATRIPLA to BIKTARVY® in HIV-1 infected adult subjects who are virologically suppressed (HIV-1 RNA < 50 copies/mL).

4.2. Study Design

This protocol describes a prospective study involving the switch of HIV infected patients currently on ATRIPLA® that are virologically suppressed (HIV-1 RNA < 50 copies/mL) to BIKTARVY® and monitoring them over a 48-week period.

4.3. Sample Size

All patients meeting eligibility will be included in the study, the expected sample size being a total number of subjects: 100 HIV-infected adults.

4.4. Target Population

HIV-1 infected adults (≥ 18 years) with HIV-1 RNA < 50 copies/mL on a stable ATRIPLA® regimen prior to screening.

4.5. Eligibility Criteria:

4.5.1. Inclusion Criteria.

Subjects must meet all, of the following criteria:

- ≥18 years of age
- HIV positive
 - On a stable antiretroviral regimen consisting of ATRIPLA® for at least the 6 consecutive months
 preceding Screening Visit.
- Plasma HIV-1 RNA concentrations at undetectable levels for at least 6 consecutive months prior to the screening visit and have HIV RNA< 50 copies/mL at the Screening Visit.
- Estimated GFR ≥30mL/min according to the Cockcroft-Gault formula for creatinine clearance.
- Hepatic transaminases (AST and ALT) ≤5x upper limit of normal (ULN)
- Total bilirubin ≤1.5 mg/dL, or normal direct bilirubin.
- Adequate hematologic function (hemoglobin ≥ 8.5g/dL; platelets ≥ 50,000/mm³; absolute neutrophil count ≥1,000/mm³)
- Female subjects of reproductive potential using a reliable and consistent method of birth control for at least three months prior to study dosing. Male subjects should use condoms when engaging in intercourse of reproductive potential.
- The ability to understand and sign a written informed consent form, which must be obtained prior to initiation of study procedures.

4.5.2. Exclusion Criteria

- A new AIDS-defining condition diagnosed within 30 days prior to screening.
- Individuals with decompensated cirrhosis. (i.e. ascites, encephalopathy, etc.)
- Pregnancy
- A history of malignancy within the past 5 years (prior to screening) or ongoing malignancy other than
 cutaneous Kaposi's sarcoma (KS), basal cell carcinoma, or resected, noninvasive cutaneous squamous
 carcinoma. Individuals with cutaneous KS are eligible but must not have received any systemic therapy for
 KS within 30 days prior to baseline.
- Active, serious infections (other than HIV-1 infection) requiring parenteral antibiotic or antifungal therapy within 30 days prior to baseline.
- Life expectancy < 1 year.
- Subject participation in any clinical trial without prior approval from the Investigator.
- Concomitant use of disallowed agents from Table 2
- Participation in any other investigation study 30 days prior to enrollment.

4.6. Risks/ Benefits

There are potential risks for adverse reactions and for patient intolerance to the investigational drug. Benefits include the potential loss of neuropsychiatric effects of efavirenz as well as the documented reduced nephrotoxicity and bone mineral loss with switching from TDF to TAF.

5. STUDY DATA

Demographic summaries will include sex, race/ethnicity, age, prior antiviral therapies and (if available) pertinent prior mutations. Data relevant to endpoint evaluation includes subject HAART regimen, viral load (VL), CD4 T-cell count, fasting lipid panel, serum creatinine, PRO, at initial screening, weeks 4, 8, 12, 24, 36 and 48.

6. STUDY DRUG/STUDY PROCEDURES

6.1 STUDY DRUG

6.1.1 Formulation

The BIKTARVY® (BIC/FTC/TAF 50/200/25 mg) tablets are capsule-shaped, film coated purplish-brown, debossed with "GSI" on one side of the tablet and "9883" on the other side of the tablet. Each tablet core contains 50 mg of bictegravir, 200 mg of emtricitabine, and 25 mg of tenofovir alafenamide. In addition to the active ingredients the BIKTARVY® tablets contain croscarmellose sodium, magnesium stearate, and microcrystalline cellulose. The tablet cores are film-coated with iron oxide red, iron oxide black, polyethylene glycol, polyvinyl alcohol, talc, titanium dioxide.

6.1.1.1 Packaging and Labeling

BIKTARVY® is packaged in white, high density polyethylene (HDPE) bottles. Each bottle contains 30 tablets, silica gel desiccant and polyester packing material. Each bottle is enclosed with a white, continuous thread, child-resistant polypropylene screw cap with an induction-sealed and aluminum-faced liner.

6.1.1.2 Storage and Handling

Study drug will be stored at controlled room temperature of 25°C (77°F); excursions are permitted between 15°C and 30°C (59°F and 86°F). Storage conditions are specified on the label. Until dispensed to the subjects, all bottles of study drugs should be stored in a securely locked area, accessible only to those authorized site personnel.

To ensure the stability and proper identification, study drug should not be stored in a container other than the container in which they were supplied. Keep the bottle tightly closed to protect from moisture.

Consideration should be given to handling, preparation, and disposal through measures that minimize drug contact with the body. Appropriate precautions should be followed to avoid direct eye contact or exposure through inhalation when handling.

6.1.2 Dosage and Administration

BIKTARVY® will be provided by Gilead. Study drug is taken once daily, at approximately the same time every day. Each BIKTARVY® tablet contains 50mg of bictegravir (BIC), 200mg of emtricitabine (FTC), and 25mg of tenofovir alafenamide (TAF).

6.1.3 Prior and Concomitant Medications

With the following exceptions, subjects should continue to receive treatment for other conditions, prophylactic vaccines as per local medical guidelines and primary provider recommendations.

The use of medications for the treatment of HIV, other than the study drug, is prohibited.

Medications and herbal/natural supplements listed in the following table are disallowed or should be used with caution while subjects are participating in the study. Subjects will refrain from consumption of grapefruit juice and Seville orange juice throughout participation in the study.

Table 1 Prior and Concomitant Medications

Drug Class	Use for a minimum of 2 hours before and 2 hours after any dose of study drug
Antacids	Tums or Rolaids
Buffered medications	The ulcer medication sucralfate (Carafate), supplements that contain calcium, iron or zinc
Drug Class	Agents Disallowed must be discontinued at least 30 days prior to the Day 1 visit and for the duration of the study.
Antiarrhythmic Agent	Dofetilide
Anticonvulsants	Phenobarbital, Phenytoin, Carbamazepine, Oxcarbazepine
Antimycobactrerials	Rifampin, Rifapentine, Rifabutin
Antiretrovirals	Any antiretroviral that is not part of the study regimen
GI motility Agents	Cisapride
Herbal/Natural Supplements	St. John's Wort, Echinacea

If subjects need to initiate treatment with any excluded concomitant medication, the Investigator must be consulted prior to initiation of the new medication.

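### Read literally, the Table 1 header over antacids and buffered medications directs use around each dose, which does not fit the restrictive framing of section 6.1.3

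*Combined protocol and SAP*

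**What the plan says.** Section 6.1.3 opens: "With the following exceptions, subjects should continue to receive treatment for other conditions". The contents of the table are thus set up as exceptions, that is, as limits on what subjects may go on taking. The sentence that introduces Table 1 then says that products "listed in the following table are disallowed or should be used with caution while subjects are participating in the study".

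Table 1 has two blocks, each with its own header.

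- The first block has the header "Use for a minimum of 2 hours before and 2 hours after any dose of study drug". Under it are antacids ("Tums or Rolaids") and buffered medications ("The ulcer medication sucralfate (Carafate), supplements that contain calcium, iron or zinc").
- The second block has the header "Agents Disallowed must be discontinued at least 30 days prior to the Day 1 visit and for the duration of the study". Under it are the named antiarrhythmic, anticonvulsant, antimycobacterial, antiretroviral, GI motility and herbal agents.

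**The concern.** The first header is an affirmative instruction. Its verb is *use*, and neither the header nor the two rows under it contain a word of restriction. A table introduced as restrictive therefore appears to direct use at exactly the times around dosing that it singles out.

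Two things are at stake. The first is what subjects are told: the section itself treats these products as needing restriction or caution, so the direction of the instruction matters for their safety. The second is how conduct is classified. Concomitant medication is reviewed at every visit (Appendix 1), and section 7.6.2.2 says that inappropriate use of prohibited concomitant medication may be documented as a protocol deviation. Staff need to know which behaviour the table asks for before they can record a departure from it.

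**Working it through.** No arithmetic applies, and the two-hour figures are not in dispute. The check is to compare the texts and then look for anything elsewhere that settles the direction of the instruction.

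**Step 1. Header against the section's framing.**

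| Text in section 6.1.3 | Direction |
|---|---|
| Opening sentence | Table items are exceptions to continuing other treatment: restrictive |
| Sentence introducing the table | Items are either not allowed or allowed with caution: restrictive, in two tiers |
| Header of the second block | Agents must be stopped: restrictive, stated outright |
| Header of the first block | Products are to be used around any dose: affirmative, no restricting word |

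Three of the four texts restrict and one directs use. The second header shows that the table can state a restriction plainly, so the first header is the one out of line.

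**Step 2. Search for text that resolves it.**

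- Section 6.1.2 (dosage) says only: "Study drug is taken once daily, at approximately the same time every day". It gives no timing relative to other products.
- Sections 6.2.2.2 and 6.2.2.3 (Day 1 and treatment visits) describe counselling on adherence and on a consistent time of day. They do not mention antacids, sucralfate or supplements.
- Section 7.6.2.2 says how inappropriate use of prohibited medication may be documented, but not what counts as inappropriate for these products.
- Appendix 1 schedules the medication review but gives no rule to review against.
- Section 4.5.2 excludes "Concomitant use of disallowed agents from Table 2", but the only table in the list of in-text tables is Table 1. This is a separate cross-reference error. It matters here only because following the reference does not help the reader.

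Nothing found settles the point. Table 1 is the only source of timing for these products.

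**Step 3. Consequence for classification.** Take a subject who records a calcium supplement within two hours of a dose.

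- If the two-hour periods are periods of use, this follows the header.
- If they are periods of non-use, this departs from it.

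The same record is compliance under one reading and a deviation under the other, and the protocol does not say which reading applies.

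**The case against.** Four arguments weigh against the point.

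**A word may have been lost.** The text was read from a PDF, tables are the part most easily damaged, and one missing leading word would remove the problem. The header survives as a continuous phrase with no gap or redaction mark, but a dropped first word would leave the same result. Loss is neither shown nor excluded, so the point is conditional on the source page.

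**The introduction does not forbid these products.** It sets two tiers, and since the second block is headed as disallowed, the first block is naturally the cautious-use tier, in which some use is permitted. A reader might infer that the header and the introduction give opposite instructions. That is too strong, because permitted use with a timing condition fits the cautious tier. What stands is narrower: permitting cautious use is not the same as directing use around each dose.

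**Staff may read the header as a spacing rule.** The restrictive opening makes this plausible, and a literal duty to take sucralfate or iron around every dose, even with no reason to, would be odd. Even so, the reader has to set aside the printed verb, and the reference to a minimum period attaches grammatically to use.

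**The consequences are easily overstated.** A reader might infer that subjects would take restricted products around every dose for 48 weeks, or that virologic failures could no longer be attributed to the regimen. The documents support neither. They do not say that subjects are counselled from Table 1, and they state no interaction or consequence for these products. These objections limit the claim, but none of them supplies the missing direction.

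**Conclusion.** The point holds as an internal wording inconsistency in an operative instruction. As printed, the first header of Table 1 directs use around each dose. That does not fit the section's description of the table items, and no other text resolves it. The practical result is that staff cannot tell from the protocol whether taking these products near a dose is compliance or a deviation.

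Its size is limited. It has no bearing on the sample size, the snapshot definition or the descriptive primary analysis. A reader might be tempted to put a share of the roughly 100 subjects on it, but the documents say nothing about how many take antacids, sucralfate or mineral supplements, or how many would act on the literal wording, so no number can be given.

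The conclusion assumes that the source page carries the header as it appears in the text. If a restricting word stands there, the point falls. It is worth acting on because it concerns an instruction affecting subjects, there is no backup text, and it is cheap to settle.

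**What to change.** 1. Check the Table 1 header on the source page for a missing word. If a restricting word is there, nothing further is needed.
2. If the header stands as printed, the sponsor and investigator should reconcile it with the introductory sentence of section 6.1.3. The header should say explicitly whether the two-hour periods are periods of use or of non-use. Which it should be is a clinical matter for them, and no rule is proposed here.
3. Carry the corrected wording into any site material copied from the table.

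The cost is a one-line wording change, plus the IRB submission and approval that section 9.3.1 requires for protocol modifications. The wrong table number in section 4.5.2 can be corrected in the same amendment.

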6.2.5.1 Management of Viral Rebound

Subjects who meet either of the criteria listed below will be considered to have virologic rebound:

- At any post Day 1 Visit, an HIV-1 RNA ≥ 50 copies/mL which is subsequently confirmed at the following visit (scheduled or unscheduled)
- Any subject with HIV-1 RNA ≥ 50 copies/mL at study drug discontinuation

Following the unconfirmed virologic rebound, subjects will be asked to return to the clinic for a blood draw, 4 weeks after the date of the original test that had an RNA ≥50 copies/mL. If virologic rebound is confirmed

[figure not shown]
and the HIV-1 RNA is \geq 200 copies/mL, the blood sample from the confirmation visit will be the primary sample used for HIV-1 genotypic and phenotypic testing. After a subject's first post-baseline resistance test, additional testing will be conducted on a case-by-case basis. Any subject may be discontinued at Investigator's discretion or per local treatment guidelines.

If no resistance is detected from the genotype or phenotype, the subject may remain on study drug and HIV-1 RNA test should be again repeated 2-3 weeks later. If HIV-1 RNA \geq 50 copies/mL remains Investigators should carefully evaluate the risks and benefits of remaining on study drug and document this assessment in the on-site medical record.

Subjects who are nonadherent on an ongoing basis will be considered for discontinuation per the Investigator's discretion or local treatment guidelines. Sub-investigators who opt to discontinue study drugs for an individual subject must discuss with the Investigator prior to study drug discontinuation.

For subjects who are off study drug but remain in study, it will be the Investigator's discretion to manage virologic rebound.

Figure 1

6.2.5.2 Subjects with HIV-1 RNA ≥ 50 copies/mL at Study Drug Discontinuation or Week 48

Subjects with HIV-1 RNA \geq 50 copies/mL at Study Drug Discontinuation, last Visit, or Week 48 will be considered virologic failures. Subjects with HIV-1 RNA \geq 50 copies/mL at Week 48 will be asked to return for an unscheduled visit within 4 weeks for a retest as detailed in Section 6.2.5. Subjects with HIV-1 RNA \geq 200 copies/mL will also have resistance testing as detailed in Section 6.2.5.

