7.6.2.2 Reporting Other Special Situations

Any inappropriate use of concomitant medications prohibited by this protocol should not be reported as "misuse," but may be more appropriately documented as a protocol deviation.

Refer to Section 7.3 for full instructions on the mechanism of special situation reporting.

All clinical sequelae in relation to these special situation reports will be reported as AEs or SAEs at the same time using the AE EMR and/or the SAE report form. Details of the symptoms and signs, clinical management, and outcome will be reported, when available.

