8.5.1.1 US FDA-defined Snapshot Algorithm

All HIV-1 RNA data collected on-treatment (i.e. including data collected up to 1 day after the last dose date of the study drug) will be used in the snapshot algorithm. Virologic outcome will be defined as the following categories:

- HIV-1 RNA < 50 copies/mL: subjects who meet this criteria by result of the last available ontreatment laboratory result in the Week 48 analysis window
- HIV-1 RNA ≥ 50 copies/mL: subjects who meet this criteria by result of the last available ontreatment laboratory result in the Week 48 analysis window or do not have laboratory results in the Week 48 window and who discontinue study drug either:
 - due to lack of efficacy or
 - for reason other than lack of efficacy and have the last available on-treatment HIV-1 RNA ≥ 50 copies/mL
- No virologic Data in the Week 48 Analysis Window: subjects who do not have on-treatment HIV-1 RNA data in the Week 48 window because
 - Discontinuation of the study drug for reason other than lack of efficacy and have the last available on-treatment HIV-1 RNA < 50 copies/mL or
 - Missing data during the Week 48 window but remain on study drug

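### The Week 48 snapshot in 8.5.1.1 counts HIV-1 RNA below 50 as a success even when a non-study antiretroviral was taken alongside BIKTARVY

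*Combined protocol and SAP*

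**What the plan says.** **Medication rules.** Section 6.1.3 states: "The use of medications for the treatment of HIV, other than the study drug, is prohibited". Table 1 in that section puts "Any antiretroviral that is not part of the study regimen" among the agents disallowed throughout the study. The section then closes with: "If subjects need to initiate treatment with any excluded concomitant medication, the Investigator must be consulted prior to initiation of the new medication". It gives no outcome of the consultation and no consequence for study drug or for analysis. Section 7.6.2.2 says that inappropriate use of a prohibited medication "may be more appropriately documented as a protocol deviation". Section 6.2.2.5 does not list an added antiretroviral as a reason to stop study drug; noncompliance appears there only as a discretionary reason.

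**Endpoint rules.** Section 8.5.1.1 admits to the snapshot "All HIV-1 RNA data collected on-treatment (i.e. including data collected up to 1 day after the last dose date of the study drug"). Where the Week 48 window holds a result, the subject is placed below 50 or at 50 and above "by result of the last available ontreatment laboratory result in the Week 48 analysis window". No category mentions other antiretrovirals. Section 8.2.2 keeps every dosed subject in the full analysis set, and no per-protocol set or sensitivity analysis is defined.

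**Data.** Section 5 says: "Data relevant to endpoint evaluation includes subject HAART regimen, viral load (VL), CD4 T-cell count". Appendix 1 schedules a concomitant medication review at every visit.

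**The concern.** The objective is the virologic outcome of switching to BIKTARVY. A suppressed result obtained on BIKTARVY plus another antiretroviral does not answer that question, yet the algorithm as written cannot tell it from suppression on BIKTARVY alone. If the second drug was added because BIKTARVY was not holding the viral load, a failure is recorded as a success. That lowers the primary proportion (50 and above) and raises the first secondary proportion (below 50). The study has a single cohort, so no control arm would carry a similar error.

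The regimen is named as relevant to the endpoint in Section 5, but the algorithm never uses it. A prohibition tells the site what not to do; it does not tell the analyst how to classify someone who breaches it.

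**Working it through.** **Step 1. Is there a plan figure to reproduce?** No. Sections 4.3 and 8.8 give about 100 subjects without an expected rate, margin, power or precision target, and 8.5.1 describes the primary analysis as descriptive. The check is therefore a trace of the classification, followed by arithmetic for scale.

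**Step 2. Trace.** Take a subject who starts a non-study antiretroviral to treat HIV, keeps taking BIKTARVY, and has a Week 48 window result obtained after that start. Call the addition failure-related if it was made for lack of efficacy or if the last on-treatment RNA before it was 50 or above.

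| Week 48 RNA | Addition | Class as written | Class if on-treatment data end before the addition | Change in below-50 proportion | Change in 50-and-above proportion |
|---|---|---|---|---|---|
| below 50 | failure-related | below 50 | 50 and above | −1 point | +1 point |
| below 50 | other reason | below 50 | no virologic data | −1 point | 0 |
| 50 and above | failure-related | 50 and above | 50 and above | 0 | 0 |
| 50 and above | other reason | 50 and above | no virologic data | 0 | −1 point |

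Changes are per subject at n = 100: 1/100 = 1.0 percentage point. The first row is the one that matters most. The last row shows that the effect on the primary proportion is not one-directional in every case.

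**Step 3. Scale.** Neither the failure count nor the number of affected subjects is in the documents, so both are assumed here. The plan specifies no confidence interval; exact (Clopper-Pearson) 95% limits are used only to show size. For x events in n = 100, the lower limit is the 0.025 quantile of Beta(x, n − x + 1) and the upper limit is the 0.975 quantile of Beta(x + 1, n − x). Assume one failure counted as written, and k further subjects of the first-row type:

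- k = 0: 1/100 = 1%, interval 0.03% to 5.45%
- k = 1: 2/100 = 2%, interval 0.24% to 7.04%
- k = 2: 3/100 = 3%, interval 0.62% to 8.52%

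**Step 4. How likely is at least one affected subject?** With an assumed per-subject rate p, the chance among 100 is 1 − (1 − p)^100. This gives 39% at p = 0.5%, 63% at 1%, 87% at 2% and 99% at 5%. The documents support no particular value of p.

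**The case against.** The strongest reply is that the plan already forbids the situation. The ban on other HIV drugs in 6.1.3 carries no exception, and 7.6.2.2 treats such use as a likely deviation. **This stands as an argument about frequency.** It does not settle classification, because a subject who breaches the ban remains in the full analysis set and is classed by the Week 48 result.

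A reader might infer that the closing sentence of 6.1.3 lets excluded drugs be started. The documents do not support that. The sentence imposes a duty to consult and grants no permission, and most of the other classes in Table 1 treat conditions other than HIV, where a consultation step has an obvious purpose. The analysis gap does not depend on this sentence: an unapproved addition is classed in the same way.

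A reader might also infer that the rebound pathway leads to an added drug. Section 6.2.5.1 says "If no resistance is detected from the genotype or phenotype, the subject may remain on study drug", which is conditional, and it never describes adding an antiretroviral. If study drug is instead stopped for lack of efficacy and there is no on-treatment Week 48 result, 8.5.1.1 already classes the subject at 50 and above. A subject with confirmed rebound also remains a virologic failure under 6.2.5, although Sections 3.2 and 8.1.2 do not list that as a separate endpoint.

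The primary analysis is descriptive, so no test or margin could change its result. That limits the consequence, but the proportion is itself the reported finding. Finally, the endpoint refers to the FDA snapshot. Whether that outside source addresses added antiretrovirals cannot be checked here; the algorithm written out in 8.5.1.1 does not.

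**Conclusion.** The point holds as a gap in 8.5.1.1: suppression on BIKTARVY plus a non-study antiretroviral is classed as below 50. No other section closes the gap. Where the drug was added for lack of efficacy and the Week 48 result is below 50, the error favours BIKTARVY in both the primary and the first secondary endpoint.

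The size is limited and unknown. Each such subject is worth 1 percentage point at n = 100. With very few failures, which is an assumption, one subject is visible in the estimate, but the illustrative intervals for 1/100 and 2/100 overlap almost entirely. It would go too far to say that every case biases in one direction, that the protocol authorises the addition, or that a material number of cases is expected. The change is worth making because it is cheap and can be fixed before the data are seen.

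**What to change.** **In 8.5.1.1**, add a rule for a subject who starts a non-study antiretroviral to treat HIV while still on study drug:

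- On-treatment data for the snapshot end the day before that start. A Week 48 window result obtained before then still decides the class.
- Otherwise use the existing categories: 50 and above if the drug was added for lack of efficacy or the last earlier on-treatment RNA was 50 or above; if neither applies, no virologic data.
- Do not apply the rule to an isolated or accidental dose, so that valid Week 48 data are not discarded.
- List all affected subjects, and report the classification as now written as a sensitivity analysis.

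**In the concomitant medication review**, record the start date and the reason for any non-study antiretroviral. The plan provides for regimen data and a review at each visit, but does not state that these two items are captured.

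**Separately**, the prohibition and Table 1 in 6.1.3, the closing consultation sentence of that section, and 6.2.2.5 must be reconciled. No position is taken on which clinical rule is right.

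**Cost.** A few sentences, two data fields and one listing with a sensitivity table. The below-50 proportion may be slightly less favourable. A subject in the last row of the table would leave the 50-and-above count, which the listing and sensitivity analysis would make visible.
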